### **Inclusion Criteria**

- Patient gives informed consent to participate in the study
- Patient is undergoing a primary total knee arthroplasty.
- Age > 18 and <80 years old.

### **Exclusion criteria**

- Patient lacks the capacity to consent to the research project (study will not utilize LAR signatures during the informed consent process)
- Weigh < 100 pounds
- BMI > 38
- Pregnancy or suspected pregnancy
- Past medical history of opioid addiction.
- Established hypersensitivity (ie allergy) to morphine.
- Acute or chronic liver disease for example cirrhosis.
- Use of any narcotics 5 days before surgery (opioids, hydrocodone, morphine, hydromorphone, fentanyl, etc).
- Undergoing bilateral total knee replacement, revision total knee arthroplasty, or any additional procedure outside of a primary total knee arthroplasty.
- Unable to get general and spinal anesthesia.
- Same-day discharge on day of surgery.

We will access the following data from medical records (Epic) including PHI:

- MRN, date of surgery, age, gender, past medical history, height, weight, BMI, laterality, pre-operative ROM, pre-operative pain VAS, intra-operative tourniquet pressure, procedure duration, and medications received during hospital stay.

Post-operatively we will ask study patients in both groups to complete a post-op symptom journal that will collect the following information in the interim before the patient's standard 2 week post op appointment with [name], [name], or [name]:

- Record daily pain levels using a validated pain scale for 14 days post op.
- Record daily pain medication use for days 14 post-op.
- Record daily nausea levels using a validated scale as well as recording bowel movements and any instances of emesis for 7 days post op.

Additionally, the tourniquet pressure intra-op will be standardized to 275 mmHg across all 3 providers on the research team (Drs. [name], [name], and [name]). This falls within the normal standard of care for all 3 providers for their total knee arthroplasty patients. However, it has been shown in the literature that tourniquet pressure can influence acute post-operative muscle quality including increased pro-inflammatory cytokines. Therefore, to limit outside factors on post-operative inflammatory marker levels as well as post-operative rehabilitative outcomes the research team will use the same tourniquet pressure for all study patients. This does not reflect an elevation in risk for study patients since 275 mmHg falls within range of standard of care for total knee arthroplasty patients for all 3 providers.

### **Baseline and Post-op Blood Samples:**

Systemic sample – Blood draws will only be done with [name] patients that decide to participate in the study if they are the first or second case of the day. Three blood draws will be taken in these patients including just after induction of anesthesia, 15 minutes after the tourniquet is released, and 10 hours post op. The 10hr post-op blood draw timing will be based on the timing of the intraosseous injection. Serum samples will be used to measure inflammatory cytokines IL-6 and IL-8, and expression of CD11a, CD11b, CD11c, and CD18 as well as the systemic level of morphine present in the blood. Only these specific study patients will be having blood draws done due to the 10 hr post-op draw needing to be processed within 30 minutes of the draw. Blood samples will be collected in EDTA glass tubes by Houston Methodist nursing staff or a qualified member of the research team (eg. physician, fellow, or resident). Up to 10 ml of blood will be collected per time point.

For our primary outcome variable of VAS recorded pain, power analysis was performed using JMP statistics software utilizing data extracted from prior work done on the average VAS-Pain scores for TKA patients.

The statistical model for this investigation to be utilized in this investigation is a 2(Treatment) x 2(Time-point) mixed model analysis of covariance with repeated measures, co-varied on pre-operative VAS scores recorded on the day of surgery. Although there will be several days of VAS recorded out to 14-days post-surgery, the statistical question for pairwise comparisons will be to determine (1) how pain recorded on each subsequent day compares back to initial baseline (pre-operative) values within each group (treatment vs control) and (2) how each group compares to each other at the same measurement time-point. Therefore, each subsequent day will be modeled separately against the baseline value.

From the reference cited above, the 3-day average VAS score immediately following TKA was 3.2 cm (standard deviation, 2.0cm). The minimum detectable change (MDC) to detect will be set at 1.6cm as described in the literature.

The primary hypotheses of the study is that the treatment group will experience a reduction in post-operative pain compared to the control group. Based on the previous literature listed above, for a power analysis of 2 groups across 2 time-points, to detect a MDC of 1.6cm at a statistical

power of 0.9 ( $\alpha=0.05$ ), we will require a total of 35 patients per group (total of 140 observations). To account for a potential patient dropout rate of ~20%, we will aim to recruit 42 patients per group for a total of 84 patients.

The aforementioned statistical analysis will be performed at the end of each year to evaluate the efficacy of the intervention and to identify potential outliers in the data or any possible errors in data entry. Yearly analysis using the same statistical modeling will also be performed for our secondary outcome measures (tissue biomarkers) in order to prevent potential tissue sample and biochemical reagent degradation over time and to confirm the accuracy of the tissue analysis procedure performed.

Additionally, the study will stop recruiting if adverse effects is significantly different between the two treatment groups, or greater than the previously specified risks listed within the informed consent and protocol or if a new unanticipated adverse effect is discovered. Recruitment will be suspended if there are 5 similar adverse events in a row. The most serious risks include respiratory depression, apnea, circulatory depression, respiratory arrest, shock, and cardiac arrest. These risks are <1% of the population. More frequent adverse effects include sedation, lightheadedness, dizziness, nausea, vomiting, and constipation. Patients will be monitored for these side effects in the immediate post-operative period.

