## 1. Purpose of the Study / Objectives

The purpose of this study is to determine if IO morphine decreases pain, inflammatory markers, and post-operative opioid use in total knee arthroplasty (TKA) patients.

- Aim 1: IO morphine will significantly reduce patient pain in the post-operative period after primary TKA.
  - Sub aim: IO morphine will cause significantly higher levels of morphine within the joint compared to current standard of care.
- Aim 2: IO morphine will decrease systemic inflammatory markers in the post-operative period after primary TKA.
- Aim 3: IO morphine will result in significantly less post-operative oral opioid use, and achieve superior outcomes such as increased range of motion (ROM).

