## 2. Background

Following total knee arthroplasty (TKA), orthopedic surgeons must provide medication to control postoperative pain. Pain can be due to inflammation caused from tissue trauma, or nerve injury. Traditionally, opioids have been used as the sole pain management medication. Opiates reduce pain levels because they bind to opioid receptors inside and outside of the central nervous system. However, because the underlying physiology of pain is both neurogenic and inflammatory, the medications given should be multimodal. For example, cyclooxygenase-2-specific anti-inflammatory agents that are given pre-operatively, inhibit prostaglandin synthesis, and therefore decrease inflammation and pain in the immediate post-operative period.

Prior studies have explored if tissue or intra-articular injections with pain medications have effects on post-operative pain levels. Compared to patients with no intra-operative pain medication injection, patients that had intra-articular or soft tissue injections of a combination of bupivacaine, epinephrine, and morphine, had significant better pain control in the immediate post-operative period. Other studies have demonstrated that after receiving intra-articular injections, the need for post-operative narcotics decreased.

Though there are studies that have proven a beneficial effect of intra-operative medications, there have also been multiple studies that did not detect any difference in pain ratings in the immediate post-operative period. Therefore, it is still widely debated among orthopedic surgeons if intra-articular injections of pain medications reduces pain, decrease inflammation, and reduced use of opioids in the post-operative period.

Though studies have examined the effect of intra-articular morphine injection on pain, they have not determined if the level of morphine in the bone is higher compared to levels obtained intravenously. In addition, studies have not demonstrated if morphine has an effect on the inflammatory environment post-operatively. However, following cardiopulmonary bypass surgery, it was determined that morphine decreases the inflammatory response after surgery. Levels of a variety of inflammatory cytokines (IL-6, IL-8, CD11a, CD11b, CD11c, and CD18) were decreased among the patients that received morphine compared to patients that did not.

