## Study Intervention

This study is evaluating whether a 10mg intraosseous injection of morphine will help reduce inflammatory markers following surgery as well as reduce pain and pain medication use in patients undergoing primary total knee arthroplasty when compared with patients receiving the current standard of care for primary total knee arthroplasty. In the post-operative period study patients will have their post-operative opioid consumptions monitored while in the hospital and for 14 days following their surgery. Study patients will not be allowed Ketorolac or Celecoxib (Toradol), both non-steroidal anti-inflammatories (NSAIDs), in the PACU / post-operative period following their total knee replacement. This is being done because the research team wishes to standardize the post-operative care protocols across all 3 providers participating in the study since not all prescribe NSAIDs in the post-operative period following TKA. Additionally, there is no method for NSAIDs like Ketorolac or Celecoxib to be converted into morphine equivalence scores and thus would prevent accurate quantification of pain relief provided in the post-operative period.

Should the patient suffer any side-effects from the IO morphine injection they will have all of the necessary care provided to them. This study will require the patient to consent to a number of study-related items including that do not fall under their usual standard of care:

- Filling out study surveys (PROMIS Global Health SF v1.1 and KOOS JR) at pre-op, 2 weeks post op, 8 weeks post op, and 1 year post-op. The surveys will be sent through RedCap.
- Blood draws to measure systemic levels of inflammatory cytokines right after induction of anesthesia, 15 minutes post tourniquet release, and 10 hours post op. This sample will be collected by a qualified Houston Methodist nurse or qualified member of the research team (ie physician/fellow/resident).

- Filling out a symptom journal for 2 weeks post op that will record pain, pain medication use, nausea (including emesis), and bowel movements.
- Lastly, patient range of motion will be recorded from their physical therapist' progress notes and at 2 week post-operative follow-up appointment.

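### Aim 2 blood markers: the plan names serum but draws only into EDTA tubes, and assigns CD11a, CD11b, CD11c and CD18 expression to a cell-free specimen

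*Combined protocol and SAP*

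**What the plan says.** Aim 2 in Section 1 is that "IO morphine will decrease systemic inflammatory markers in the post-operative period after primary TKA". The aim does not list the markers. The panel that the trial will measure is set out only in Section 3, under Baseline and Post-op Blood Samples: "Serum samples will be used to measure inflammatory cytokines IL-6 and IL-8, and expression of CD11a, CD11b, CD11c, and CD18". The same sentence adds the systemic morphine level, so serum is the stated specimen for seven analytes.

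The same paragraph specifies the collection: "Blood samples will be collected in EDTA glass tubes". The draws are "just after induction of anesthesia, 15 minutes after the tourniquet is released, and 10 hours post op", and the volume is given as "Up to 10 ml of blood will be collected per time point". The one handling detail is the reason for restricting the draws to one surgeon's earliest cases of the day: the "10 hr post-op draw needing to be processed within 30 minutes of the draw". What that processing consists of is not described.

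Two other places bear on the panel. Section 2 (Background) reports a cardiac-surgery study in these terms: "Levels of a variety of inflammatory cytokines (IL-6, IL-8, CD11a, CD11b, CD11c, and CD18) were decreased". The Study Intervention list describes the sampling as "Blood draws to measure systemic levels of inflammatory cytokines right after induction of anesthesia" and at the two later times, with no matrix or assay.

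**The concern.** The paragraph has two faults, and the second matters more.

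First, the tube and the specimen do not match. Serum is the fluid left after blood has clotted, and EDTA prevents clotting.

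Second, the specimen does not match the measurement. IL-6 and IL-8 are soluble and can be assayed in a cell-free fluid. The four CD molecules are integrin subunits carried on leukocytes, and the plan's own word for what it wants from them is expression. A cell-free sample, whether serum or plasma, could at best give shed soluble forms, which is a different measurement with a different unit.

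At stake is the interpretation of most of the Aim 2 panel. If the stated matrix is followed, a result reported as CD11/CD18 expression would either not exist or would be something else under that name. Surface expression also could not be recovered later from a sample that had been kept only as cell-free fluid.

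**Working it through.** No sample-size, power or alpha figure enters this point, and the plan gives no figure to reproduce. The check sets the statements side by side and counts markers.

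**Inputs from the documents**
- Specimen: serum, for all six markers and morphine (Section 3, blood samples).
- Tube: EDTA glass, the only type named (same paragraph).
- Draws: 3 per sampled patient, up to 10 ml each (same paragraph).
- Time limit: 30 minutes, stated for the 10-hour draw only (same paragraph).
- Cell-containing blood aliquot, plasma, flow cytometry or any other assay: none named in any section.

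**Inputs from general laboratory knowledge, not stated in the documents**
- EDTA is an anticoagulant, so an EDTA tube gives whole blood or, once spun, plasma.
- CD11a, CD11b, CD11c and CD18 are leukocyte surface molecules, and serum and plasma are cell-free.

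**Step 1: tube against specimen.** The EDTA tube cannot produce the serum that the text calls for. This applies to all seven analytes.

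**Step 2: specimen against measurement**

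| Analyte | Stated specimen | What is measured | Obtainable from the stated specimen? | Obtainable from the EDTA blood drawn? |
|---|---|---|---|---|
| IL-6, IL-8 | serum | soluble level | yes in principle, but no serum is collected | yes, as EDTA plasma |
| Morphine | serum | systemic level | yes in principle, but no serum is collected | yes, as EDTA plasma |
| CD11a, CD11b, CD11c, CD18 | serum | expression | no; soluble forms at best | yes, if a cell-containing aliquot is kept and assayed |

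**Step 3: count.** Six inflammatory markers are named, and 6 − 2 = 4 of them are CD molecules. 4/6 = 67% of the panel has a stated specimen that cannot give the stated measurement. Over 3 draws that is 4 × 3 = 12 of 6 × 3 = 18 marker-by-time values per sampled patient. This is a count of measurements. It says nothing about bias or power, and the plan states no power for any biomarker.

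**The case against.** The strongest reply is that the blood is right and only a word is wrong. Up to 10 ml of anticoagulated blood contains the leukocytes needed, and a 30-minute limit is compatible with fresh-cell work. The sampling paragraph also separates the cytokines IL-6 and IL-8 from the expression of the CD markers, so its authors may have had a cell assay in mind. The sentence in Section 2 that calls all six cytokines describes another study and is not a sampling instruction. All of this stands, and it limits the point. It does not remove it, because serum is the specimen assigned to those four markers and nothing else in the plan tells a laboratory to keep or assay cells.

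Three stronger readings are tempting, and the documents do not support them.

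- A reader might infer that the four markers cannot be obtained from this trial's samples at all. The EDTA blood drawn can supply them.
- A reader might infer that the plan directs the laboratory to spin each sample, keep the supernatant and discard the cells. The text mentions no centrifugation, discarding or storage of supernatant. The loss of cells is a risk of following the stated matrix, not a written instruction.
- A reader might infer that IL-6 and IL-8 will come from a mixture of serum and plasma because some staff will change tubes. One tube type is named for every draw, and nothing suggests a switch.

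It is also fair to say that Aim 2 is not the primary outcome. The sample size rests on VAS pain alone.

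**Conclusion.** The plan is wrong as written on this point, within a limited scope. It assigns seven analytes to a specimen that its only named tube cannot yield. It also assigns the expression of four of the six inflammatory markers to a cell-free specimen, with no cell aliquot or cell assay named. For IL-6, IL-8 and morphine the error is mainly a label, since EDTA plasma can be used. For the four CD markers it is a substantive error in the measurement rule, not only missing detail.

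The scope is Aim 2 in the patients who have blood drawn. The primary VAS pain analysis is unaffected. The conclusion rests on the two items of laboratory knowledge listed in the working, and on the plan's word expression meaning expression on cells. If soluble forms were intended, the plan should say so, because that is a different endpoint.

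**What to change.** In Section 3, under Baseline and Post-op Blood Samples:

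1. Replace serum with EDTA plasma as the specimen for IL-6, IL-8 and morphine at every draw.
2. Add that, at each of the three draws, an aliquot of EDTA whole blood is set aside before any centrifugation, and that surface expression of CD11a, CD11b, CD11c and CD18 is measured on it by a named cell-based assay, for example flow cytometry.
3. State the assay and unit for each marker, and a handling time that the laboratory confirms for all three draws. The present 30-minute limit covers only the 10-hour draw and should not be assumed to extend to the others. The laboratory should also confirm that its assay suits EDTA blood.
4. If fresh-cell assay capacity is not available, drop the four CD markers, or relabel them as soluble forms, and restrict the Aim 2 claim to IL-6 and IL-8.
5. Bring the Study Intervention list into line, since it now mentions only cytokines.

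Cost: no extra visit or draw is needed, because the aliquot comes from blood already being taken. The real cost is fresh-cell assay work at each draw, including the one 10 hours after the injection. The plan already restricts sampling because of processing capacity, and the documents do not show whether the site has this assay. The alternative costs four markers in the Aim 2 claim.

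### Aim 2 is one directional claim resting on six equal-standing markers at two post-baseline draws, with no deciding comparison and no adjustment, so the chance of a false result favouring morphine is well above 2.5%

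*Combined protocol and SAP*

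**What the plan says.** Section 1 states the aim as one hypothesis with a direction: "Aim 2: IO morphine will decrease systemic inflammatory markers in the post-operative period after primary TKA". It names no marker and no time point.

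Section 3, under the heading on baseline and post-operative blood samples, lists the assays: "Serum samples will be used to measure inflammatory cytokines IL-6 and IL-8, and expression of CD11a, CD11b, CD11c, and CD18". Systemic morphine is measured as well, but it is not an inflammatory marker. Blood is taken "just after induction of anesthesia, 15 minutes after the tourniquet is released, and 10 hours post op", so there is one baseline draw and two later ones. Only one surgeon's first and second cases of the day are sampled, and the size of that subset is not given.

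The statistical text that follows is written for VAS pain, the primary outcome. One of its two pairwise questions is "how each group compares to each other at the same measurement time-point". It continues: "Therefore, each subsequent day will be modeled separately against the baseline value". The modelling is then extended: "Yearly analysis using the same statistical modeling will also be performed for our secondary outcome measures (tissue biomarkers". The only significance level in the document is the one in the VAS sample-size sentence: "power of 0.9 ( $\alpha=0.05$ ), we will require a total of 35 patients per group".

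No lead marker, lead draw, composite, testing order or multiplicity adjustment appears anywhere.

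**The concern.** A single claim can be met in many ways. If any marker at either later draw is lower on morphine at p<0.05, nothing in the plan prevents that result from being reported as confirming Aim 2, and nothing says that the other comparisons count against it. The choice of deciding comparison can therefore be made after the data are seen.

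This matters more because the marker data come from a subset of unstated size with no power calculation of its own. In such a subset, one isolated favourable p-value is weak evidence but could carry the whole aim. What is at stake is the interpretation of Aim 2 only. The pain comparison has its own outcome and its own sample-size basis.

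**Working it through.** **The plan's own figure.** The documents give no sample size or error rate for Aim 2, so the only figure to reproduce is the VAS sample size. The inputs from Section 3 are a difference of 1.6 cm, SD 2.0 cm, alpha 0.05 and power 0.9.

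- Two-sided: n = 2 × (1.960 + 1.282)² × (2.0/1.6)² = 2 × 10.51 × 1.5625 = 32.8, so 33 per group (34 with the t distribution). The plan states 35, which is close.
- One-sided: n = 2 × (1.645 + 1.282)² × 1.5625 = 26.8, so 27, which does not match.

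The stated 0.05 is therefore best read as two-sided. I carry that level over to the markers as an assumption.

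**Number of comparisons.** 6 markers × 2 post-baseline draws = 12 between-group tests per analysis. The documents do not state this count. It follows if the per-time-point pain modelling is applied to each marker. Within-group changes from baseline are left out, because surgery itself may move the markers.

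**Independent tests, no true effect, one analysis.** Aim 2 predicts a decrease, so the relevant event is a significant result in morphine's favour, which has probability 0.025 per test.

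- Favouring morphine: 1 − 0.975^12 = 26.2%.
- Either direction: 1 − 0.95^12 = 46.0%.

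**Correlated tests.** The documents give no correlations, so the values below are assumed. I simulated 12 jointly normal test statistics. The correlation between different markers at different draws is the product of the two values shown.

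| Between markers | Between draws | Favouring morphine | Either direction |
|---|---|---|---|
| 0 | 0 | 26% | 46% |
| 0.3 | 0.5 | 21% | 40% |
| 0.5 | 0.5 | 18% | 35% |
| 0.7 | 0.5 | 14% | 28% |
| 0.8 | 0.8 | 10% | 21% |

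Using t-tests with an assumed 14 patients per arm (a third of 84, split in two) changes the correlated rows by about one percentage point at most. The comparators for a single pre-named test are 2.5% and 5%.

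**Yearly repeats.** With two equally spaced unadjusted looks (assumed), the chance of at least one result favouring morphine is about 40% if the tests are independent, 27% at correlations 0.5/0.5 and 16% at 0.8/0.8. In either direction the figures are about 65%, 51% and 32%.

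**Error rate under possible remedies, one analysis, two-sided.**

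- One named comparison at 0.05: 5%.
- Holm across all 12, first step 0.05/12 = 0.00417: 1 − (1 − 0.00417)^12 = 4.9% if independent, and at most 5% otherwise.
- A lead comparison at 0.05 plus Holm on the other 11 with no gate between them: 1 − 0.95 × (1 − 0.05/11)^11 = 9.6% if independent. This does not hold 5%, so the gate is needed.

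**The case against.** The strongest reply is that the count of 12 tests at 0.05 is not in the document. The level 0.05 belongs to the VAS sample size. The sentence extending the model refers to tissue biomarkers and is justified by degradation of tissue samples, while the revision history says that bone and soft-tissue collection was removed. The model is also written with pre-operative VAS as its covariate. The extension may therefore be residual text that was never meant for the blood markers. This stands as a limit on the figures, which are conditional on that reading. It does not remove the concern. If the sentence does not cover the blood markers, Aim 2 has no stated analysis at all, and the choice of marker and draw is freer still.

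A second reply is that the markers are secondary, so formal adjustment is optional and cautious reporting would do. Much of this is fair, and an exploratory label would be an acceptable answer. But the protocol gives no such label. It states a directional aim, and the Study Intervention text in Section 3 puts reduced inflammatory markers first among the things being evaluated.

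A third reply is that correlated markers give less inflation. That is true and is allowed for in the table. Even at 0.8 the favourable-direction rate is about four times 2.5%.

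**Conclusion.** The concern holds in a limited form. Aim 2 has no deciding comparison and no multiplicity control. Under the inferred 12 tests at two-sided 0.05, the chance of a false result favouring morphine in one analysis is 26% if independent and about 10% to 21% over the correlations assumed, against 2.5% for one test. In either direction it is 46%, or about 21% to 40%. Unadjusted yearly repeats would raise all of these.

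The documents do not support three stronger readings that a reader might infer:

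- **That a false positive is likely.** Even under independence the either-direction figure stays below one half in a single analysis. It passes one half only with repeated looks, and not at high correlation with two or three looks.
- **That 46% is the risk to Aim 2.** A marker that is higher on morphine cannot confirm a claimed decrease, so the favourable-direction figure is the relevant one.
- **That the markers must be analysed on a log scale.** The documents say nothing about their distribution, and four of the six are described as expression.

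The primary pain conclusion is unaffected. This is something the plan should correct, not a flaw that undermines the trial.

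**What to change.** Before any unblinded marker analysis, state which one marker at which one draw decides Aim 2, tested at two-sided 0.05. The choice is the sponsor's. For the other 11 comparisons, either label them exploratory, with estimates and confidence intervals and no claim from a single p-value, or test them by Holm only if the lead comparison is significant. Alternatively, apply Holm across all 12 and claim Aim 2 only for comparisons that survive it.

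The same text should say that the marker model applies to the blood markers, with each marker's own baseline as covariate. It should also say which analysis decides Aim 2, because the error rates above are for one look and yearly repeats would need their own control.

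The cost is a few sentences, with no change to patients, sampling or sample size. The downside is small: an isolated p<0.05 in a non-lead marker could no longer be claimed as confirming Aim 2. Under Holm across all 12, each comparison would also face a stricter threshold, starting at 0.00417, in a subset that may be small.

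### Pre-operative VAS is both a response time-point and the covariate in the primary model, so with one pooled residual variance the same-day group comparison has about 11–17% type I error instead of 5%

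*Combined protocol and SAP*

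**What the plan says.** The statistical text sits in Section 3 (Study Design), under the sub-heading on baseline and post-operative blood samples. It specifies a "2(Treatment) x 2(Time-point) mixed model analysis of covariance with repeated measures, co-varied on pre-operative VAS scores recorded on the day of surgery". Two questions are to be answered by pairwise comparison. Question 1 is "how pain recorded on each subsequent day compares back to initial baseline (pre-operative) values within each group (treatment vs control"). Question 2 is "how each group compares to each other at the same measurement time-point". The text concludes that "each subsequent day will be modeled separately against the baseline value".

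The primary hypothesis is that "the treatment group will experience a reduction in post-operative pain compared to the control group". The sample-size statement is that "we will require a total of 35 patients per group (total of 140 observations").

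The plan does not give a covariance structure, say whether the residual variance may differ between time-points, or state a pre-operative SD or a pre/post correlation. It also does not say which effect (same-day contrast, group-by-time interaction or treatment main effect) tests the primary hypothesis.

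**The concern.** A baseline score can be adjusted for, or it can be modelled as the first repeated measurement. Here it does both jobs in the same model. In every baseline row the response is the covariate itself, so once a slope b is fitted the residual is just (1 − b) times the centred baseline score. Such rows say nothing about the noise in post-operative pain, yet under a pooled variance they enter the residual variance on equal terms with the post-operative rows.

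The primary hypothesis concerns a group difference in post-operative pain, and question 2 is the comparison that addresses it. If its standard error is too small, a morphine effect is declared too often when there is none. This applies to each test, before any allowance for 14 days of comparisons or for the yearly analyses.

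**Working it through.** **1. The plan's own figures.** The difference is 1.6 cm, the SD 2.0 cm, alpha 0.05 (two-sided assumed) and power 0.9. Then n = 2 × (1.960 + 1.282)² × (2.0/1.6)² = 32.8, so 33 per group; the exact t calculation gives 34. Power at 35 is 0.91. The 35 per group is not in dispute.

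**2. Which two time-points?** 35 patients × 2 groups × 2 time-points = 140 observations, the plan's count. If baseline were a covariate only, each day's model would have 70. Question 1 also needs baseline as a response level.

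**3. Same-day contrast with one pooled variance.** Set the post-operative SD to 1, the pre-operative SD to q and the correlation to r. Both q and r are assumptions.

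- The fitted slope averages 1 (baseline rows) and r/q (post-operative rows): b = (1 + r/q)/2. The estimate is therefore midway between the change-score and ANCOVA estimates.
- True per-arm variance of the adjusted day-k value: T = (1 − r²) + (r − q)²/4.
- Variance the model uses: M = (1 − r²)/2 + (r − q)²/4.
- Type I error = 2 × [1 − Φ(1.96 × √(M/T))].

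Worked case, q = 1 and r = 0.3: T = 0.91 + 0.1225 = 1.0325 and M = 0.455 + 0.1225 = 0.5775. T/M = 1.788, the SE is too small by a factor of 1.337, and the type I error is 14.3%.

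Type I error for r = 0 / 0.3 / 0.5 (simulation: 20,000 null trials per setting, 35 per group, compound symmetry):

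| q | Formula (%) | Simulation (%) |
|---|---|---|
| 0.5 | 15.4 / 16.3 / 16.6 | 15.5 / 16.8 / 16.6 |
| 1.0 | 12.9 / 14.3 / 15.0 | 13.0 / 14.2 / 15.1 |
| 1.5 | 10.6 / 11.6 / 12.1 | 10.9 / 11.4 / 12.2 |

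At q = 1 with r = 0.7 and 0.9 the formula gives 15.7% and 16.3%. A separate covariate slope per time-point does not help while the variance stays pooled: the baseline residuals are then exactly zero, M = T/2, and the error is 16.6%.

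**4. Other readings of the same model.**

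- *Group-by-time interaction.* The covariate cancels and the raw change-score difference remains. If the patient variance component may go negative, size is about 5%. Power for 1.6 cm uses a change SD of 2.0 × √(1 + q² − 2rq). For r = 0 / 0.3 / 0.5 it is 0.65 / 0.80 / 0.91 at q = 1, 0.84 / 0.91 / 0.97 at q = 0.5, and 0.43 / 0.58 / 0.71 at q = 1.5.
- *Interaction with that component bounded at zero.* The true variance of the change, (1 − r²) + (r − q)², is set against 2s², where s² = [(1 − r²)/2 + var(change)/2]/2. At q = 1, r = 0 this is 2 against 1.5, giving 9.0%. For r = 0 / 0.3 / 0.5 the error is 9.0 / 7.5 / 6.7% at q = 1, 6.3 / 5.2 / 5.0% at q = 0.5, and 11.3 / 10.3 / 9.8% at q = 1.5. The bound matters: at q = 1 the fitted component was negative in over 99.9% of simulated trials.
- *Treatment main effect.* It estimates half the day-k effect, 0.8 cm for a true 1.6 cm. Unbounded, size is about 5%. Bounded, it is 1.6 / 2.6 / 3.9% at q = 1.
- *Separate variances per time-point.* As the slope approaches 1 the baseline residual vanishes and the likelihood has no maximum. In one simulated trial the log-likelihood term was −62, 74, 235, 396 and 557 at slopes 0.3, 0.9, 0.99, 0.999 and 0.9999.

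**5. The remedy.** ANCOVA on the post-operative score simulated at 4.8–5.2% for q = 0.5, 1 and 1.5 and r from 0 to 0.7. Its power at 35 per group is 0.91 / 0.93 / 0.97 for r = 0 / 0.3 / 0.5. A paired within-arm test for question 1 simulated at 5.1–5.2% (q = 1).

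**The case against.** The strongest reply is that several readings of the model are sound in size. With an unbounded patient variance, the main-effect estimate and its standard error are both exactly half those of the post-operative ANCOVA. Its t statistic, p-value and power are therefore identical, and that reading already delivers the recommended test on a rescaled estimate. The unbounded interaction holds 5%. With separate variances the contrast tends to a change-score comparison, which also held about 5%. The plan lists question 2 among its pairwise comparisons without calling it primary, and it never specifies a pooled variance. The correlation and SD ratio are assumed. That the covariate and the baseline response are one measurement is inferred, not stated.

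Most of this is correct, and it makes the inflation conditional. It does not rescue the plan. Question 2 is the only between-group pain comparison that the analysis paragraph names, while the main effect and the interaction are not named at all. The main effect would report half the real difference, and the separate-variance fit has no maximum likelihood solution, so what the software returns is unpredictable. The single-measurement inference is safe, because the data list in Section 3 has only one pre-operative pain VAS. Over the correlations and SD ratios tried, the pooled same-day contrast was always at least twice the nominal 5%.

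**Conclusion.** The concern holds and should be corrected before analysis. The double use of pre-operative VAS follows from the plan's own wording and its observation count. The size of the harm rests on three assumptions: the same-day contrast is the primary test, one residual variance is pooled over both time-points, and the test is two-sided at 0.05. Under these, type I error is about 13–15% at equal SDs and about 11–17% for SD ratios 0.5 to 1.5, for correlations 0 to 0.5. That is two to three times nominal. Under other readings the size runs from below nominal to about 11%, with an estimate that may be halved and power that may fall well short of 0.9. As written, the trial's conclusion could turn on a software default.

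**What to change.** For the between-group question, make post-operative VAS the only response and pre-operative VAS a covariate only. State that the adjusted between-group difference in post-operative VAS is the primary test. Answer question 1 separately, for example with a paired comparison in each arm.

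Alternatively, use one model for both questions: baseline as a response only, no baseline covariate, a common baseline mean across arms and an unstructured covariance.

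Name the covariance structure in either case. The cost is a short rewording of the analysis paragraph and, under the first option, one added paired analysis. The sample size and data collection do not change.
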